Name of Sponsor/Company:

CytoDyn, Inc.

Name of Study Product:

leronlimab (PRO 140) - Humanized monoclonal antibody to CCR5

Protocol Number:

CD07_TNBC

Indication:

Metastatic Triple Negative Metastatic Breast Cancer (mTNBC)

Note: Patients will be followed from the start of treatment until 2 years post-treatment or death, whichever occurs first, and average survival time will be measured.

- The number, frequency, and severity of AEs collected from the time of first treatment until 12 weeks after study treatment completion to evaluate safety of leronlimab (PRO 140) and carboplatin in subjects with CCR5+ mTNBC.

Exploratory Outcome (Endpoints) Measures:

- Measure immune biomarkers (PD-L1) in CTCs, metastatic tissue and immune cells such as CAMLs and correlate with therapeutic benefit (PFS); and
- Correlation between CCR5 expression (CTCs, CAMLs) and PD- L1 expression.

Safety Assessments:

Safety will be assessed by close monitoring and timely assessment of adverse events (AEs), laboratory parameters (blood tests, urinalysis), vital signs (blood pressure, heart rate), subject's medical condition (physical examination including weight), general well-being and activities of daily life (Eastern Cooperative Oncology Group (ECOG) performance status). Each subject will be regularly assessed in each cycle for potential AEs and disease related signs and symptoms. The CTCAE v5.0 will be used to grade toxicities/AEs.

Statistical Considerations:**Sample Size Determination and Rationale:**

This is a Phase Ib/II, multicenter study that will enroll up to 18 subjects in Phase Ib and 30 subjects in Phase II of the study. The sample size for Phase Ib is based on conventional 3+3 study design and Phase II is based on clinical judgment. No statistical power calculation is used to establish the sample size.

Analysis Populations:

The **Intent-to-Treat (ITT) population** is defined as the set of subjects who have received at least one dose of leronlimab (PRO 140) and have measurable disease at baseline. The ITT population will be used as the primary analysis population.

The **Per Protocol (PP) population** is defined as the set of subjects who meet the ITT population requirements, were not associated with any major protocol violations and have received at least 2 cycles of treatment. This population will be identified before the database lock.

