5.1 REMOVAL OF SUBJECTS FROM STUDY TREATMENT AND/OR STUDY AS A WHOLE

Subjects can be taken off the study treatment and/or study as a whole at any time at their own request, or they may be withdrawn at the discretion of the investigator for safety, behavioral or administrative reasons. The reason(s) for discontinuation must be clearly documented on the appropriate eCRF and may include:

- Subject voluntarily withdraws from treatment (follow-up permitted)
- Subject withdraws consent (no follow-up permitted)
- Subject is unable to comply with protocol requirements
- Subject demonstrates disease progression
- Subject experiences unacceptable toxicity
- Treating physician determines that continuation on the study would not be in the subject's best interest
- Subject becomes pregnant
- Subject develops a second malignancy that requires treatment which would interfere with this study
- Subject becomes lost to follow-up (LTf)

If a subject fails to return for the scheduled study visit or is discontinued from the study, an attempt will be made to determine the reason(s). If the subject is unreachable by telephone, a registered letter will be sent to the subject requesting that he/she contact the clinic.

All patients with an ongoing SAE at the Post-Study (Follow-up) Visit (scheduled or premature) must be followed until the event is resolved (with or without sequelae) or deemed stable.

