5.3 DATA COLLECTED FROM WITHDRAWN SUBJECTS

Every attempt should be made to collect follow-up information. The reason for withdrawal from the study will be recorded in the source documents and on the appropriate page of the CRF.

Before a subject is identified as lost-to-follow up, the site should make all reasonable efforts to contact the subject. These attempts must be documented and should include at a minimum one phone call and one certified letter.

In the event that a subject is withdrawn from the study at any time due to an adverse event or SAE, the procedures stated in [Sections 9.2](#) and [9.4](#) must be followed.

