Note: Overall response rate defined as the proportion of patients who achieve an overall response of complete response or partial response in the total number of evaluable patients, assessed by RECIST v1.1. Clinical benefit rate is defined as the proportion of patients who achieve an overall response of complete response or partial response or stable disease in the total number of evaluable patients, assessed by RECIST v1.1. Imaging scans to be done at the end of 2 cycles (i.e., every 6 weeks) for the first 6 cycles (18 weeks) and at the end of 3 cycles (i.e., every 9 weeks) thereafter.

- Time to new metastases (TTNM);

Note: Recorded time from baseline metastatic disease (at time of enrollment) to the time of development of new metastasis in different site. New metastases in same site will be also recorded.

- The change from baseline in circulating tumor cells (CTC) level in the peripheral blood.

Note: Reported unit of measure will be the number of CTCs/milliliter. CTCs enumeration will be performed at baseline and at the time of response assessment. Fraction of baseline positive and change from ≥ 5 CTCs will be recorded and reported.

- Overall survival defined as time in months from the date of first study treatment to the date of death;

Note: Patients will be followed from the start of treatment until 2 years post-treatment or death, whichever occurs first, and average survival time will be measured.

- The number, frequency, and severity of AEs collected from the time of first treatment until 12 weeks after study treatment completion to evaluate safety of leronlimab (PRO 140) and Carboplatin in subjects with CCR5+ mTNBC.

Exploratory Outcome (Endpoints) Measures:

- Measure immune biomarkers (PD-L1) in CTCs, metastatic tissue and immune cells such as CAMLs and correlate with therapeutic benefit (PFS); and

- Correlation between CCR5 expression (CTCs, CAMLs) and PD- L1 expression.

PFS will be calculated using Kaplan-Meier curves and the median PFS will be read from this curve. Response rates (overall response rate, clinical benefit rate) will be calculated using proportions and 95% confidence intervals. Time to new metastases and overall survival will also be analyzed using Kaplan-Meier curves. Exploratory serial blood markers will be related to PFS using Cox regression, and to response using logistic regression.

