7.3 Handling of Missing Data

All data will be used as observed, and no imputations will be made for any missing data point. All summaries will be based on observed data only.

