8.3 Analysis of Secondary Outcome Measures

8.3.1 PFS according to RECIST v1.1 in participants with Detectable Programmed Death-Ligand 1 (PD-L1)

PFS according to RECIST v1.1 in participants with Detectable Programmed Death-Ligand 1 (PD-L1) will be calculated using Kaplan-Meier curves, and the median PFS will be read from this curve. Note: The PD-L1 expression testing will be performed at baseline. Breast tissue (primary or metastatic site) collected to analyze for the presence of CCR5 at pre-screening will additionally be used for evaluating PD-L1 expression levels.

8.3.2 Overall response rate (ORR) and clinical benefit rate (CBR) in subjects with CCR5+ mTNBC treated with leronlimab (PRO 140) and carboplatin

Overall response rate (ORR) and clinical benefit rate (CBR) in subjects with CCR5+ mTNBC treated with leronlimab (PRO 140) and carboplatin will be calculated using proportions and 95% confidence intervals.

Note: Overall response rate defined as the proportion of patients who achieve an overall response of complete response or partial response in the total number of evaluable patients, assessed by RECIST v1.1. Clinical benefit rate is defined as the proportion of patients who achieve an overall response of complete response or partial response or stable disease in the total number of evaluable patients, assessed by RECIST v1.1. Imaging scans to be done at the end of 2 cycles (i.e., every 6 weeks) for the first 6 cycles (18 weeks) and at the end of 3 cycles (i.e., every 9 weeks) thereafter.

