8.3.3 Time to new metastases (TTNM)

Time to new metastases (TTNM) will be calculated using the formula in Section 7.9.3 and summarized descriptively. Kaplan-Meier analysis will be used to depict the median time (days) to new metastases.

Note: Recorded time from baseline metastatic disease (at time of enrollment) to the time of development of new metastasis in different site. New metastases in same site will be also recorded.

8.3.4 The change from baseline in circulating tumor cells (CTC) level in the peripheral blood The change from baseline in circulating tumor cells (CTC) level in the peripheral blood will be

calculated for each subject at each timepoint and summarized descriptively.

Note: Reported unit of measure will be the number of CTCs/milliliter. CTCs enumeration will be performed at baseline and at the time of response assessment. Fraction of baseline positive and change from ≥ 5 CTCs will be recorded and reported.

8.3.5 Overall survival defined as time in months from the date of first study treatment to the date of death

Overall survival defined as time in months from the date of first study treatment to the date of death will be presented using proportions and 95% confidence intervals.

Note: Patients will be followed from the start of treatment until 2 years post-treatment or death, whichever occurs first, and average survival time will be measured.

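### SAP 8.3.5 replaces the protocol's Kaplan-Meier analysis of overall survival with unspecified proportions, with no time point, denominator or censoring rule

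*SAP*

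**What the plan says.** - **Protocol, synopsis (Statistical Methodology) and Section 8.7.3.1:** "Time to new metastases and overall survival will also be analyzed using Kaplan-Meier curves".
- **SAP 8.3.5:** OS, defined as a time in months from first study treatment, "to the date of death will be presented using proportions and 95% confidence intervals".
- **SAP 8.3.2, response rate and clinical benefit rate:** these two binary outcomes in patients given leronlimab and "carboplatin will be calculated using proportions and 95% confidence intervals".
- **SAP 8.3.3, time to new metastases:** "Kaplan-Meier analysis will be used to depict the median time (days) to new metastases". SAP 8.2.2 and 8.3.1 also keep Kaplan-Meier for PFS.
- **OS note in the protocol synopsis, Protocol 8.7.3.1, SAP 2.4.2 and SAP 8.3.5:** follow-up runs to 2 years post-treatment or death, "whichever occurs first, and average survival time will be measured".
- **SAP 7.3:** no imputation, and "All summaries will be based on observed data only".
- **Protocol 5.1:** loss to follow-up is a listed reason for removal, and so is "Subject withdraws consent (no follow-up permitted").

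**The concern.** OS is a time-to-event outcome, and some patients will have no death date. A proportion can be computed from such data only after three choices: the time it refers to, who is in the denominator, and what happens to patients whose status at that time is unknown. SAP 8.3.5 makes none of them. The detailed censoring rules in SAP 8.2.2 cover PFS only, and the formula in SAP 7.9.3 needs an event date. The protocol has no OS censoring rule either; it leaves detail to the SAP (Sections 8 and 8.7).

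The protocol puts time to new metastases and OS in one Kaplan-Meier sentence. The SAP keeps the method for the first and drops it for the second without comment. Two programmers could follow the SAP faithfully and report different OS figures, and the choice could be made after the open-label data are seen. The promised average survival time has the same gap: a patient alive at last contact has no survival time to average.

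**Working it through.** The plan states no OS figure, so there is none to reproduce. The text comparison above establishes the departure. The calculation below only shows how much the unspecified choices could matter.

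**Inputs.** Median survival of 9-12 months is the background figure in Protocol 1.5. N=30 is the Phase II sample size (SAP 3). The rest is assumed, because the documents give no loss rate or survival shape: exponential survival; a fraction p = 0.10 or 0.30 of patients given a potential loss time U, uniform on 0-24 months; loss unrelated to prognosis.

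**Formulas.** Rate r = ln 2 / median and S(t) = exp(-rt). At time t:

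- known alive A = (1-p)·S(t) + p·(1-t/24)·S(t)
- known dead D = (1-p)·(1-S(t)) + p·E[1-S(min(U,t))]
- unknown = 1 - A - D
- crude proportion with unknowns excluded = A/(A+D)
- crude proportion with the lost counted as alive = 1 - D

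**Worked case: median 12, p = 0.30, t = 24.** S = 0.25 and E[1-S(U)] = 1 - 0.75/(24 × 0.05776) = 0.459. So A = 0.70 × 0.25 = 0.175, D = 0.70 × 0.75 + 0.30 × 0.459 = 0.6627, and unknown = 0.1623. Unknowns excluded: 0.175/0.8377 = 20.9%. Lost counted as alive: 1 - 0.6627 = 33.7%. The true value is 25.0%.

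**Results at 24 months (%).**

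| Median (months) | p | Status unknown | True OS | Unknowns excluded | Lost counted as alive |
|---|---|---|---|---|---|
| 12 | 0.10 | 5.4 | 25.0 | 23.8 | 27.9 |
| 12 | 0.30 | 16.2 | 25.0 | 20.9 | 33.7 |
| 9 | 0.10 | 4.6 | 15.7 | 14.9 | 18.7 |
| 9 | 0.30 | 13.7 | 15.7 | 12.8 | 24.7 |

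The 10-30% is the share given a potential loss time. Many of these patients die first, so only about 5-16% have unknown status at 24 months.

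**At 12 months**, excluding unknowns gives 49.3% and 47.7% against 50.0% (median 12), and 39.0% and 37.4% against 39.7% (median 9), so it is low by about 1-2 points.

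**Kaplan-Meier on the same model.** In 6,000 simulated trials of 30 per scenario, mean 24-month estimates were 24.96-24.98% (median 12) and 15.64-15.79% (median 9), in line with the true values.

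**Sampling error.** The 95% half-width is 1.96·√(S(1-S)/30): 15.5 points at 25.0% and 13.0 points at 15.7%. Every shift in the table is smaller.

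**Average survival time.** Assume 5 months of treatment, so 29 months of follow-up, and no loss. Then S(29) = 0.187 (median 12) or 0.107 (median 9), which leaves about 5.6 or 3.2 of 30 patients alive. A mean over deaths only is 1/r - 29·S(29)/(1-S(29)) = 10.6 or 9.5 months. The mean restricted to 29 months is (1-S(29))/r = 14.1 or 11.6 months.

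**The case against.** **The SAP does not exclude Kaplan-Meier.** A Kaplan-Meier survival probability at a fixed time is a proportion with a confidence interval, and the protocol delegates detail to the SAP. This stands in part: the text is an unexplained departure that leaves the method open, not a ban on Kaplan-Meier. It does not supply the missing time point, denominator or censoring rule.

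**SAP 7.3 might seem to decide the matter.** A reader might infer that the observed-data rule requires patients of unknown status to be excluded. It does not. Kaplan-Meier with censoring also imputes nothing and uses only observed data, so 7.3 fits either reading.

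**Kaplan-Meier is not unbiased unconditionally.** This stands. It needs loss to be unrelated to prognosis, and consent withdrawal may not be. If the death hazard doubles after loss (an assumption; median 12, p = 0.10 and 0.30), true 24-month OS is 23.85% and 21.56%. Kaplan-Meier still gives 25.0%, while excluding unknowns gives 23.8% and 20.9%, which is closer. Even so, the crude proportion is biased when loss is harmless, and Kaplan-Meier is not.

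**The follow-up limit does no harm at these times.** This also stands. Planned follow-up is 2 years after treatment stops, so every patient has at least 24 months from first dose. Without loss, crude 12- and 24-month proportions are unbiased. The bias therefore depends on loss, and Protocol 5.3 says that before a patient is called lost "the site should make all reasonable efforts to contact the subject".

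**A deaths-only average is hypothetical.** Neither document says that the average is taken over deaths only; it may be loose wording for the Kaplan-Meier median. What stands is that no rule is given.

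**Conclusion.** The point holds as a specification fault that should be corrected before database lock. SAP 8.3.5 departs without explanation from the protocol's named method for a listed secondary outcome, and what it substitutes cannot be carried out without choices that neither document makes. Among the readings it allows are crude proportions that err at 24 months by about 1-4 points low or 3-9 points high, given exponential survival with a 9-12 month median, non-informative loss and 5-16% of patients with unknown status. The average survival time is undefined for patients still alive, and would be too low if taken over deaths only.

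A reader might infer that the trial's OS result will be materially wrong. The documents do not support that. They give no loss rate, a Kaplan-Meier reading remains open, and the illustrated shifts are below the sampling error of 30 patients. OS is descriptive, is not among the Phase II objectives (Protocol 2, SAP 2.3) and carries no formal test (SAP 5). The primary endpoint and the sample size are unaffected.

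**What to change.** In SAP 8.3.5, restore the protocol's Kaplan-Meier analysis of OS, measured from first dose. The protocol says no more than that, so the following are additions proposed here: censor patients not known to have died at the date last known alive, and report the median with its 95% CI. Kaplan-Meier survival at 12 and 24 months, with Kaplan-Meier-based intervals, is optional.

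In SAP 2.4.2 and 8.3.5, state that average survival time is reported as the Kaplan-Meier median. Align the OS note in the protocol synopsis and Section 8.7.3.1 at the next amendment; an amendment for this alone is not needed.

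The cost is minor wording in two SAP sections. No new data are needed, and Kaplan-Meier is already planned for PFS and time to new metastases.

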8.3.6 Exploratory Outcome Measures

8.3.6.1 Measure immune biomarkers (PD-L1) in CTCs, metastatic tissue and immune cells such as CAMLs and correlate with therapeutic benefit (PFS)

Immune biomarkers (PD-L1) in CTCs, metastatic tissue and immune cells such as CAMLs will be related to PFS using Cox regression.

8.3.6.2 Correlation between CCR5 expression (CTCs, CAMLs) and PD- L1 expression

CCR5 expression (CTCs, CAMLs) and PD- L1 expression will be correlated using logistic regression.

8.4 Analysis of Safety Data

All safety analyses will be conducted using the Safety population. All data collected will be summarized according to the variable type. No inferential statistics are planned.

8.4.1 Adverse Events

Adverse events will be classified by system organ class (SOC) and preferred term (PT) according to the most recent version of MedDRA dictionary.

TEAE are defined as adverse events with onset date on or after the first treatment. TEAEs will be summarized by treatment group, System Organ Class, and preferred term. The following TEAE summaries will be provided:

- a) Overall (i.e., regardless of severity or relationship to treatment)
- b) By severity grade
- c) By relationship to clinical trial treatment

Unless otherwise specified, at each level of subject summarization, a subject will be counted only once. If there is more than one occurrence of an event, the event of the worst severity or the worst-case relationship category will be summarized.

AEs leading to premature discontinuation of clinical trial treatment and Serious Adverse Events (SAEs) will also be summarized by treatment group and relationship.

All adverse events recorded in the eCRF will be presented as by-subject listings.

